## 8.1.3 DATA ANALYSIS

The study statistician will employ established approaches to develop statistical models to study the association between timeliness of access to paediatric intensive care and clinical outcomes (Objective 1.1), and the association between care delivered by PICRTs and clinical outcomes (Objective 1.2).

#### 8.1.3.1 Clinical outcomes

Primary outcome: Mortality within 30 days following PICU admission (the first admission in case of multiple PICU admissions), established by data linkage with death registrations.

Secondary outcomes to include:

- a) Mortality at fixed time-points (PICU discharge, 90 days and 1 year following [first] PICU admission)
- b) Number of PICU admissions during study period and time to readmission (if applicable)
- c) Length of stay in PICU (number of days from PICU admission to discharge, for each PICU admission)
- d) Resource use in PICU (number of days of invasive ventilation, vasoactive agent therapy, renal replacement therapy and extra-corporeal life support during PICU stay, for each PICU admission)
- e) Length of hospital stay linked to the first PICU admission (number of days from hospital admission to hospital discharge)
- f) Number of A&E attendances in the 12 months following discharge from the first PICU admission
- g) Hospital resource use (total number of days admitted to hospital) in the 12 months following discharge from the first PICU admission.

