## 8.1.2.2 Study data and generating the linked dataset

We will extract relevant PICANet data related to the transport and the PICU admission episode from all transported admissions to participating PICUs in England and Wales with an admission date during a 3-year study period (1 Jan 2014 to 31 Dec 2016). To ensure a high-quality dataset, we will apply a series of data cleaning rules including individual data range checks and inter-variable validation to the study data set to identify and clean common and obvious data quality errors prior to analysis.

We will apply for HRA CAG approval for this study. See Appendix C for data flows during the linkage process.

Data linkage will be undertaken by the NHS Digital Data Access Request Service (DARS) acting as a 'trusted third party'. PICANet have experience of successfully linking PICANet data to HES/ONS data through HSCIC in the past. The availability of NHS numbers in a very high proportion of PICANet (98%) and CMP records for children (97%) provides reassurance that most records can be successfully matched using a minimal number of patient identifiers. PICANet data, including identifiers, is currently held at the University of Leeds. University of Leeds will upload a list of patient identifiers (NHS numbers, date of birth, name and postcode) and a unique DEPICT study number to secure servers at NHS Digital for a cohort of children admitted to PICUs in England

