Matching will consider the fact that some children may be admitted to hospital (and PICU) on multiple occasions within the study period.

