## 8.1.3.2 Model 1: Timeliness of access to paediatric intensive care

Timeliness of access to paediatric intensive care will be measured by:

- a) Time from acceptance of the referral by a PICRT to arrival of the PICRT at the patient bedside, and
- b) Time from acceptance of the referral by a PICRT to arrival of the patient on the PICU.

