## 8.1.3.5 Sample size calculations

PICANet data from 2014/15 indicates that the 30-day mortality rate for transported PICU admissions is approximately 7% and that PICRTs reach critically ill children within 3 hours of referral acceptance in 85% of cases. Accounting for the potential for clustering of data by PICRTs, we calculate that a minimum of 9685 transports would allow us to detect a 3% difference in 30-day mortality between the two groups (transports taking ≥3 hours to reach patient bedside and transports taking <3 hours to reach patient bedside) with 80% power and alpha 5%. We will analyse PICANet data from transported PICU admissions over a 3-year period (nearly 15,000 transports) to ensure adequate sample size for our analysis.

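### Mortality outcomes are counted once per child, at the first PICU admission, but the dataset, exposures and sample size are counted per transport, and the protocol never aligns the two.

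*Protocol*

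**What the plan says.** All references are to the protocol.

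**Per child.** Section 8.1.3.1 sets the primary outcome as "Mortality within 30 days following PICU admission (the first admission in case of multiple PICU admissions), established by data linkage with death registrations". Secondary outcome a follows the same rule: "Mortality at fixed time-points (PICU discharge, 90 days and 1 year following [first] PICU admission". Outcomes e, f and g (hospital stay, A&E attendances, hospital days) are also tied to the first PICU admission.

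**Per transport.** Section 8.1.2.2 extracts "all transported admissions to participating PICUs in England and Wales with an admission date during a 3-year study period". The two timeliness exposures in 8.1.3.2 belong to a single referral: "Time from acceptance of the referral by a PICRT to arrival of the PICRT at the patient bedside" and "Time from acceptance of the referral by a PICRT to arrival of the patient on the PICU". The care exposures in 8.1.3.3 (team, interventions, incidents) are likewise features of one transport. Section 8.1.3.5 takes its 7% mortality from transported admissions, requires at least 9,685 transports, and continues: "We will analyse PICANet data from transported PICU admissions over a 3-year period (nearly 15,000 transports".

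**Per admission.** Outcome c is "Length of stay in PICU (number of days from PICU admission to discharge, for each PICU admission", and outcome d (days of organ support) uses the same unit.

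**Repeat admissions.** Section 8.1.2.2 recognises that "some children may be admitted to hospital (and PICU) on multiple occasions within the study period", but only as a record-matching matter. Outcome b counts a child's PICU admissions and time to readmission. Section 8.1.3.4 names random effects for PICU, PICRT and general hospital, and none for child. The synopsis refers to an index PICU admission without defining it.

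**The concern.** A regression of 30-day death on time to bedside needs one exposure and one outcome per row, both from the same illness episode. As written, the outcome exists once per child and the exposure exists once per transport. For a child transported twice, the protocol does not say whether the second transport is a row, and if it is, which outcome it carries. Nor does it say in words that the admission starting the 30-day clock must be a transported one.

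Three things depend on this. The first is the analysis set for the primary result, which also feeds the lives-saved outcome in 8.3.1 and the survival optimisation in 8.4.6. The second is the stated sample size, which is given in a unit that the primary outcome does not use. The third is the precision of outcomes c and d, where several rows can come from the same child. If the unit is left open until the linked data have been seen, it can also be chosen with results in view.

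**Working it through.** **1. Units side by side**

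| Element | Section | Unit |
|---|---|---|
| 30-day mortality; outcomes a, e, f, g | 8.1.3.1 | Child (first admission) |
| Outcomes c, d | 8.1.3.1 | Each PICU admission |
| Extract | 8.1.2.2 | Each transported admission |
| Exposures | 8.1.3.2, 8.1.3.3 | Each transport |
| 7% rate; 9,685; nearly 15,000 | 8.1.3.5 | Each transport |
| Named random effects | 8.1.3.4 | PICU, PICRT, general hospital |

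If no child recurred, these units would coincide. Section 8.1.2.2 and outcome b say that some do.

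**2. The plan's own figure.** Inputs from 8.1.3.5: 7% mortality (taken as the overall rate), 85% reached in under 3 hours, a 3-point difference, 80% power, 5% alpha (two-sided assumed). The groups are then p1 = 7% + 0.85 × 3% = 9.55% (3 hours or more) and p2 = 7% − 0.15 × 3% = 6.55%, with allocation k = 0.85/0.15. The pooled-variance formula is

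n1 = [1.96 × √((1 + 1/k) × 0.07 × 0.93) + 0.842 × √(p1(1−p1) + p2(1−p2)/k)]² / 0.03² = (0.5424 + 0.2624)² / 0.0009 = 720.

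The total is 720/0.15 = 4,800 before clustering. Reaching 9,685 needs a design effect of 9,685/4,800 = 2.02. With 10 equal PICRTs (968.5 transports each) the implied ICC is 1.02/967.5, about 0.001. Other two-sided readings of the rates, without continuity correction, give 3,267 to 5,540 and design effects of 2.96 to 1.75. The protocol states no ICC, so 9,685 is neither confirmed nor contradicted. It is a count of transports, with no step to children.

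**3. From transports to children.** The share r of transports that are not the child's first is not in the documents and is assumed here. N = 15,000 × (1 − r). Power uses the rates in step 2, once with the design effect held at 2.02 and once with the ICC held at 0.00105, so that the design effect is 1 + (N/10 − 1) × 0.00105.

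| r | N (children) | Power, design effect 2.02 | Power, ICC fixed |
|---|---|---|---|
| 0 | 15,000 | 0.93 | 0.87 |
| 5% | 14,250 | 0.92 | 0.86 |
| 10% | 13,500 | 0.90 | 0.85 |
| 20% | 12,000 | 0.87 | 0.84 |
| 30% | 10,500 | 0.83 | 0.81 |

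N falls to 9,685 when r = 1 − 9,685/15,000 = 35.4%.

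**4. Does mortality change if later transports drop out?** At 7%, 15,000 transports give 1,050 deaths. If repeat transports also have 7% mortality (an assumption), removing them takes 53, 105 or 210 deaths out with 750, 1,500 or 3,000 transports: 997/14,250, 945/13,500 and 840/12,000, each 7.0%. The rate is unchanged, because numerator and denominator fall together.

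**5. Outcomes c and d.** A child with two admissions supplies two rows. Those rows share comorbidity and severity, but no named random effect links them. Positive within-child correlation left out of the model makes standard errors too small. The amount depends on the repeat share and the correlation, and the documents give neither.

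**The case against.** The best defence is that the protocol can be read sensibly as it stands. The synopsis limits the population to children transported by a retrieval team for emergency admission and refers to an index PICU admission. Section 8.1.2.2 extracts only transported admissions. The first admission is then the first within that extract, exposure and outcome come from the same episode, and one record per child is a legitimate way to avoid within-child correlation and overlapping 30-day windows. Deaths after later transports lie outside the estimand; they are not errors. Power stays adequate at any moderate repeat share, and a statistical analysis plan that is not shown may settle the modelling.

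Most of this stands, and it rules out some stronger readings. A reader might infer that an earlier planned admission could start the clock, so that a death after a later delayed transport is scored as survival. That needs an admission outside the extract. A reader might also infer that recorded mortality would drop to 6.65%, 6.3% or 5.6% at repeat shares of 5%, 10% or 20%. That needs every later transport to stay in the denominator with the first admission's outcome, and no section says so. Step 4 shows about 7% if they are dropped. Bias towards the null is not shown either: the direction depends on how later transports are handled and on whether they differ between the delay groups.

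The defence does not remove the mismatch. The outcome definition and the sample size are both fixed in the protocol, in different units, and the reading that reconciles them is not written down. Nor does it address outcomes c and d, where repeat records stay in.

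**Conclusion.** The point holds as an inconsistency of units. On the sensible reading (first eligible transported admission per child), the primary analysis has one record per child, and the nearly 15,000 in 8.1.3.5 overstates it by an unknown amount: 750, 1,500 or 3,000 records at assumed repeat shares of 5%, 10% or 20%. The shortfall against 9,685 begins only above about 35% repeats. Power under the step 2 assumptions stays above 0.8 up to 30% repeats, whether the design effect or the ICC is held fixed. The consequence for the primary outcome is therefore an ambiguous analysis set and a misstated N, not a failed sample size. For outcomes c and d, standard errors may be too small by an amount that cannot be calculated from the protocol. No conclusion is drawn about the number of deaths lost or the direction of any bias.

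**What to change.** - **Section 8.1.3.1:** define the index admission as each child's first eligible transported PICU admission between 1 January 2014 and 31 December 2016. Take the exposure, the primary outcome and outcomes a and e to g from that episode. Use the same term in the synopsis.
- **Section 8.1.3.5:** restate the minimum and the expected sample in children, with the observed or expected share of repeat transports and the ICC behind 9,685.
- **Outcomes c and d:** limit them to transported admissions, so that every row has an exposure value, and add a child-level random effect or child-clustered standard errors in 8.1.3.4.

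The cost is a few sentences in the protocol, carried into the analysis plan. No new data are needed, because the planned extract and linkage already hold the transports and dates of death. The downside is a stated N below 15,000 and slightly wider intervals for outcomes c and d.

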# **3 STUDY SYNOPSIS**

Title	Critically ill children and young popplay do national Differences in access to			
Inte	Critically ill children and young people: do national Differences in access to			
	Emergency Paediatric Intensive Care and care during Transport affect clinical			
-	outcomes and patient experience? The DEPICT study			
Sponsor name	Great Ormond Street Hospital NHS Foundation Trust			
Primary	To study how clinical outcomes of critically ill children transported to			
objective	paediatric intensive care (PIC) are affected by national variations in			
	timeliness of access to paediatric intensive care.			
Secondary	1. To study how the experience of critically ill children (and their families)			
objective (s)	transported to paediatric intensive care are affected by national			
	variations in timeliness of access to paediatric intensive care.			
	2. To study how clinical outcomes of critically ill children transported to			
	paediatric intensive care are affected by national variations in care			
	provided by PIC retrieval teams (PICRT) during stabilisation and			
	transport.			
	3. To study how the experience of critically ill children (and their families)			
	transported to paediatric intensive care are affected by national			
	variations in care provided by PIC retrieval teams (PICRT) during			
	stabilisation and transport.			
	4. To study the relative cost effectiveness of current PICRTs.			
	5. To use mathematical modelling to evaluate whether alternative models			
	of PICRT service delivery can improve clinical and cost effectiveness.			
Study Design	Mixed methods study including a) quantitative analysis of linked routinely			
	collected PICANet audit data, b) qualitative study involving questionnaires			
	and interviews of critically ill children transported to intensive care and their			
	families, clinicians and managers, c) health economic analysis and d)			
	mathematical modelling.			
Study Endpoints	Primary outcome: 30-day mortality			
	Secondary outcomes: Mortality in PICU, at 90 days and within the first year			
	after the index PICU admission; length of stay in PICU; Resource use in PICU			
	(days on invasive ventilation, vasoactive agent therapy, renal replacement			
	therapy and extra-corporeal life support); length of hospital stay for the			
	index admission; number of hospital admissions and days in hospital in the			
Comple Ci-c	12 months following the index PICU admission.			

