## 2) Draw inferences regarding the effect of key factors on patient outcome

Before any modelling work is undertaken, we will do a thorough descriptive analysis of the datasets and look for potential issues that would need to be addressed at an early stage, such as a large proportion of missing data for key confounders or an unusual distribution of age/weight/diagnosis or other risk factors. Prior to multivariate modelling, we will explore univariate associations between key explanatory variables (timeliness, care delivered) and potential confounders with our stated primary and secondary outcomes. All explanatory variables and confounders with significant univariate association with outcome will be considered in the regression modelling for Models 1 and 2. We will develop statistical models to study the association between timeliness of access to intensive care and clinical outcomes, and the association between care delivered by PIC retrieval teams and clinical outcomes. Since we recognise that the data could potentially be clustered by PICRT, we will develop multilevel models as appropriate (to include the random effects of PICU/PICRT/general hospital) depending on the outcome:

- Mortality at fixed time-points: logistic regression
- Length of stay (PICU, hospital), resource use in PICU and hospital resource use following
   PICU discharge: linear, Poisson or negative binomial regression models (as appropriate) and survival models
- A&E attendances: Poisson or negative binomial regression model (as appropriate)

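### PICU readmissions are counted to a calendar date with unequal follow-up, and the 12-month hospital-days window has two different starts and no allowance for time alive

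*Protocol*

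**What the plan says.** Section 8.1.3.1 lists the secondary outcomes. Outcome b is "Number of PICU admissions during study period and time to readmission (if applicable". Section 8.1.2.2 draws the cohort from children "with an admission date during a 3-year study period (1 Jan 2014 to 31 Dec 2016", so the same dates govern both entry and the end of counting. By contrast, outcome a uses fixed time points, and outcomes f and g use fixed 12-month windows: "Number of A&E attendances in the 12 months following discharge from the first PICU admission" and "Hospital resource use (total number of days admitted to hospital) in the 12 months following discharge from the first PICU admission".

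The synopsis (Section 3) counts hospital admissions and hospital days over the "12 months following the index PICU admission", so its clock starts at admission and not at discharge. The medium-run economic analysis in Section 8.3.1 also runs for one year from PICU admission.

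Stay and organ support are counted in days: "Length of stay in PICU (number of days from PICU admission to discharge, for each PICU admission", and "Resource use in PICU (number of days of invasive ventilation, vasoactive agent therapy, renal replacement therapy and extra-corporeal life support during PICU stay".

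Section 8.1.3.4 (step 2) allows linear, count and survival models for stay and resource use. For the emergency department outcome it gives only "A&E attendances: Poisson or negative binomial regression model (as appropriate". It lists no model for outcome b. The only rule for children who die is the one for QALYs in Section 8.3.3.

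**The concern.** Three features of the outcome definitions need attention.

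- **Unequal time at risk.** A child who enters in January 2014 can accumulate readmissions for three years; one who enters in December 2016 has a few weeks at most. If late-reached children tend to enter at times with less remaining follow-up, they will show fewer readmissions for that reason alone. Section 4.1.2 gives one possible link, reporting that some children wait much longer during the winter surge.
- **Two starts for one window.** Hospital days over 12 months are a different quantity when counted from PICU admission than when counted from PICU discharge. The discharge start leaves a child who dies in PICU without a window, so the outcome is restricted by something that happens after the exposure. It also fails to match the economic window.
- **Time alive.** In a study that asks whether delay raises mortality, a raw 12-month total credits each early death with little or no use. A higher-mortality group can then appear to use less care although its survivors use the same amount.

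**Working it through.** The protocol gives no figure for these outcomes, so there is none to reproduce. The checks below show sizes only.

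**1. Time at risk for outcome b.** Input: the study dates in Section 8.1.2.2. Time at risk = 31 December 2016 minus entry date.

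| Entry | Days at risk |
|---|---|
| 1 Jan 2014 | 1,095 |
| 2 Jul 2015 | 548 |
| 1 Jan 2016 | 365 |
| 1 Dec 2016 | 30 |

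With entry spread evenly over the calendar (assumption), the mean is 1.50 years, and 33% of entry dates leave less than one year.

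**2. Link to season.** Section 8.1.3.4 defines summer as March to August and winter as September to February. On the same even-entry assumption, mean follow-up is 1.41 years for winter entrants and 1.59 for summer entrants: 1.41/1.59 = 0.89. This compares seasons. The contrast between late-reached and early-reached children would be smaller, because both groups contain children from both seasons.

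**3. Link to calendar year (illustration).** Section 8.1.3.5 puts 15% of transports at 3 hours or more. It gives no trend, so the yearly shares below are assumed. Mean follow-up by entry year is 2.5, 1.5 and 0.5 years, with equal numbers entering each year.

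- Shares of 12%, 15%, 18%: late group (0.12×2.5 + 0.15×1.5 + 0.18×0.5)/0.45 = 1.37 years; early group (0.88×2.5 + 0.85×1.5 + 0.82×0.5)/2.55 = 1.52 years; ratio 0.90.
- Shares of 14%, 15%, 16%: 1.46 against 1.51 years; ratio 0.97.
- Shares of 18%, 15%, 12%: 1.63 against 1.48 years; ratio 1.11.

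The bias can therefore run either way, and it is nil if the share is constant. Outcome b counts all PICU admissions. If the index admission is included, the effect on the count is diluted: at assumed rates of 0.1, 0.2 and 0.3 readmissions per child-year, (1 + rate×1.37)/(1 + rate×1.52) gives about 0.986, 0.976 and 0.968 under the first set of shares.

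**4. Deaths in the 12-month totals.** Inputs: about 7% 30-day mortality and a planned 3% difference (Section 8.1.3.5), read as percentage points and taken as 7% against 10%. Assume that early deaths contribute zero use and that survivors in both groups have the same mean use m. The ratio of group means is 0.90m/0.93m = 0.968, whatever m is. Taking 7% as the overall rate instead (6.55% against 9.55%) gives 0.9045/0.9345 = 0.968.

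**5. PICU stay.** Assume a survivor mean of 7 days and vary the stay before death d. The ratio is (0.90×7 + 0.10d)/(0.93×7 + 0.07d).

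| d (days) | Means, 10% v 7% mortality | Ratio |
|---|---|---|
| 2 | 6.50 v 6.65 | 0.977 |
| 3 | 6.60 v 6.72 | 0.982 |
| 7 | 7.00 v 7.00 | 1.000 |
| 10 | 7.30 v 7.21 | 1.012 |

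The direction depends on time to death, which the protocol does not give.

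**6. Start of the window.** Section 3 has PICU admission, outcome g in Section 8.1.3.1 has PICU discharge, and Section 8.3.1 has PICU admission. The conflict concerns hospital days only, since the synopsis does not list A&E attendances.

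**The case against.** The strongest reply is that offsets, censoring and competing events belong in the statistical analysis plan, which Section 8.1.3.4 promises and which is not shown. That is right as far as method goes. Section 8.1.3.4 already admits survival models for stay and resource use, so it would be wrong to say that the protocol commits these outcomes to plain linear or count models. What stands is that the counting window of outcome b and the two starts of the 12-month window are fixed in the protocol itself.

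Second, unequal follow-up biases a comparison of exposure groups only if exposure is related to entry date. This is correct, and the documents report no trend in response times over the years. The winter surge gives a plausible route, but season is among the candidate covariates and adjusting for it could remove part of the effect. Year of entry is not named in that list, although the list is open.

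Third, mortality is reported alongside, and outcome b is not among the synopsis endpoints. Both are true and limit the consequences.

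Stronger readings are tempting, but the documents do not support them:

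- A reader might set 2014 entrants (mean 2.5 years) against 2016 entrants (0.5 years) and infer a fivefold distortion. That compares entry years, whereas the study compares timeliness and care groups.
- A reader might infer that more deaths always make PICU stay look shorter. The direction depends on how long children live before dying.
- A reader might take the qualifier on time to readmission to exclude children who are never readmitted. The wording is equally consistent with censoring them.
- A reader might think that the cost models inherit the fault. A child who dies early does consume less, and the death is counted separately as a life lost or as zero QALYs.

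**Conclusion.** The point holds in limited form and concerns secondary outcomes only. Outcome b has follow-up from three years to almost none, with about a third of entry dates under one year (even entry assumed). The effect on the timeliness comparison is noise unless exposure is linked to entry date. Under the assumed yearly shifts, the ratio of follow-up between groups ranges from 0.90 to 1.11.

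The conflict over the start of the 12-month hospital-days window is a plain contradiction that needs no assumption, and the protocol has to settle it.

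For the raw 12-month totals, the spurious reduction is about 3% at the planned mortality difference, assuming that early deaths contribute nothing and survivors' use is equal. That is modest, but it makes the higher-mortality group look as if it uses less care. For PICU stay and organ support no direction can be claimed.

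**What to change.** 1. **Readmissions.** Analyse the count with log days alive and at risk, from index PICU discharge to 31 December 2016, as offset. Alternatively, use a fixed window limited to children who have that follow-up; a one-year window would drop about a third of entry dates. Analyse time to first readmission in all children, with death as a competing event and censoring at the end of data.
2. **Window.** Reconcile Sections 3, 8.1.3.1 and 8.3.1 on one start for the 12-month window, preferably the index PICU admission, so that deaths in PICU are included.
3. **Totals.** For A&E attendances, use log days alive and at risk as offset, leaving out inpatient days. Report hospital use as days alive and out of hospital, beside the raw total.
4. **Stay.** Use the survival models that Section 8.1.3.4 already allows, with discharge alive as the event and death as a competing event.

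Raw totals remain right for the cost analysis, and no extension of the PICANet extract is needed. The cost is outcome wording and analysis code. The drawbacks are that days alive and out of hospital combines survival with duration, so its components must be shown, and that the A&E rate describes time alive only and draws nothing from children who die in PICU.
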